**PAGE 45 OF 287** 

# 9.2.7 Registry Study Visit(s)

Visits will be in accordance with routine clinical practice (Follow-up Visits are recommended every 6 months).

The FOPal registry study will collect data at the Baseline Visit, Follow-up Visits / End of Study Visit.

The Baseline Visit can be performed by either telephone/video contact or clinic visit (preferred) as per the investigator's judgement.

# 9.2.7.1 Baseline Visit for Exposed Participants

Investigators at participating FOPal registry sites will identify participants who fulfil the inclusion and exclusion criteria. Signed informed consent should be obtained prior to enrolment according to local regulations and once inclusion and exclusion criteria have been satisfied. If the participant is <18 years old (or the legal age of consent in the jurisdiction in which the study is taking place), assent and parent or legally authorised representative consent will also be required.

The participants will attend a clinic (preferred) or telephone/video visit and assessments will be performed according to routine clinical care. The following variables will be captured from Baseline Visit records as available:

# For exposed naïve participants (Table 2)

- Baseline demographics;
- Physical examination including a general assessment as well as dermatologic, lymph nodes, head, eyes, ears, nose and throat (HEENT), chest, cardiac, abdomen, limb/extremities, musculoskeletal, neurologic and other assessments (as per routine clinical care);
- Medical or surgical history (12 months before the Baseline Visit);
- FOP history (date of symptom onset, date of diagnosis by a physician, method of diagnosis, date of genetic test if performed and type of FOP genetic variant);
- Growth status assessment for growing children (bone age, knee height and epiphyseal status assessment);
- Tanner staging for growing children;
- Linear height and weight (linear height within 6 to 12 months prior to the Baseline Visit will also be collected);
- Vital signs (respiratory rate, blood pressure and heart rate);
- Pregnancy test (as per local label, participants are assessed for child-bearing status and pregnancy prevention measures. These conditions also concern participants who are not currently sexually active unless the prescriber considers that there are compelling reasons to indicate that there is no risk of pregnancy);
- Prior (two months before the Baseline Visit) and concomitant medications;
- Concomitant surgery and non-drug therapies;
- Prior use of palovarotene (investigational product);
- Marketed palovarotene dose for chronic and flare-up treatment;
- Spirometry and DLCO test;
- CAJIS for FOP;

**PAGE 46 OF 287** 

- Movement mobility history including flare-ups (over the past 12 months prior to the Baseline Visit);
- Movement mobility history including flare-ups (from Baseline Visit);
- Spinal health assessment using radiological imaging (e.g. Computed tomography (CT), X-ray, scintigraphy, etc);
- AEs, SAEs, Special Situations and Adverse Events of Special Interest (AESIs) (following provision of the signed informed consent);
- FOP-PFQ (the adult form should be used for participants 15 years and older and for participants under 15 years old, there is a self-completed paediatric form (developed for participants 8 to 14 years old) and a proxy completed paediatric form (developed for participants 5 to 14 years old));
- PROMIS Global Health Scale (the adult form should be used for participants 15 years and older and for participants under 15 years old, there is a self-completed paediatric form (developed for participants 8 to 14 years old) and a proxy completed paediatric form (developed for participants <15 years old));
- FOP assistive devices assessment.

#### For exposed non-naïve participants (Table 3):

- Baseline demographics;
- Physical examination including a general assessment as well as dermatologic, lymph nodes, HEENT, chest, cardiac, abdomen, limb/extremities, musculoskeletal, neurologic and other assessments (as per routine clinical care);
- Medical or surgical history (12 months before the first marketed palovarotene intake);
- FOP history (date of symptom onset, date of diagnosis by a physician, method of diagnosis, date of genetic test if performed and type of FOP genetic variant);
- Growth status assessment for growing children (bone age, knee height and epiphyseal status assessment) at the first marketed palovarotene intake and at the Baseline Visit;
- Tanner staging for growing children at the first marketed palovarotene intake and at the Baseline Visit:
- Linear height and weight from the first marketed palovarotene intake and at the Baseline Visit (linear height within 6 to 12 months prior to the first marketed palovarotene intake will also be collected);
- Vital signs (respiratory rate, blood pressure and heart rate);
- Pregnancy test (as per local label, participants are assessed for child-bearing status and pregnancy prevention measures. These conditions also concern participants who are not currently sexually active unless the prescriber considers that there are compelling reasons to indicate that there is no risk of pregnancy);
- Prior (two months prior to the first marketed palovarotene intake and until the Baseline Visit) and concomitant medications;
- Concomitant surgery and non-drug therapies;
- Prior use of palovarotene (investigational product);
- Marketed palovarotene dose for chronic and flare-up treatment;
- Spirometry and DLCO test at the first marketed palovarotene intake and at the Baseline Visit:

PAGE 47 OF 287

- CAJIS for FOP at the first marketed palovarotene intake and at the Baseline Visit;
- Movement mobility history, including flare-ups (over the past 12 months prior to the first marketed palovarotene intake and until Baseline Visit);
- Movement mobility changes, including flare-ups (from Baseline Visit);
- Spinal health assessment using radiological imaging (e.g. CT, X-ray, scintigraphy, etc) at the first marketed palovarotene intake and at the Baseline Visit;
- Retrospective important medical events related to the disease (including vertebral fractures) at the first marketed palovarotene intake and until the Baseline Visit;
- AEs, SAEs, Special Situations and AESIs (following provision of the signed informed consent);
- FOP-PFQ (the adult form should be used for participants 15 years and older and for participants under 15 years old, there is a self-completed paediatric form (developed for participants 8 to 14 years old) and a proxy completed paediatric form (developed for participants 5 to 14 years old)) at the first marketed palovarotene intake and at the Baseline Visit;
- PROMIS Global Health Scale (the adult form should be used for participants 15 years and older and for participants under 15 years old, there is a self-completed paediatric form (developed for participants 8 to 14 years old) and a proxy completed paediatric form (developed for participants <15 years old)) at the first marketed palovarotene intake and at the Baseline Visit;
- FOP assistive devices assessment at the first marketed palovarotene intake and at the Baseline Visit.

#### 9.2.7.2 Baseline Visit for Unexposed Participants

Investigators at participating FOPal registry sites will identify participants who fulfil the inclusion and exclusion criteria. Signed informed consent should be obtained prior to enrolment according to local regulations and once inclusion and exclusion criteria have been satisfied. If the participant is <18 years old (or the legal age of consent in the jurisdiction in which the study is taking place), assent and parent or legally authorised representative consent will also be required.

The participants will attend a clinic (preferred) or telephone/video visit and assessments will be performed according to routine clinical care. The following variables will be captured from Baseline Visit records as available (Table 4):

- Baseline demographics;
- Physical examination including a general assessment as well as dermatologic, lymph nodes, HEENT, chest, cardiac, abdomen, limb/extremities, musculoskeletal, neurologic and other assessments (as per routine clinical care);
- FOP history (date of symptom onset, date of diagnosis by a physician, method of diagnosis, date of genetic test if performed and type of FOP genetic variant);
- Growth status assessment for growing children (bone age, knee height and epiphyseal status assessment);
- Tanner staging for growing children;
- Linear height and weight;
- Vital signs (respiratory rate, blood pressure and heart rate);

**PAGE 48 OF 287** 

#### REGISTRY STUDY PROTOCOL: VERSION 8.0: DATE 16 APRIL 2025

- Concomitant medications;
- Concomitant surgery and non-drug therapies;
- Spirometry and DLCO test;
- CAJIS for FOP:
- Movement mobility history including flare-ups (over the past 12 months prior to the Baseline Visit);
- Movement mobility changes including flare-ups (from Baseline Visit);
- Medical events of special interest (over the past 12 months prior to the Baseline Visit);
- FOP-PFQ (the adult form should be used for participants 15 years and older and for participants under 15 years old, there is a self-completed paediatric form (developed for participants 8 to 14 years old) and a proxy completed paediatric form (developed for participants 5 to 14 years old));
- PROMIS Global Health Scale (the adult form should be used for participants 15 years and older and for participants under 15 years old, there is a self-completed paediatric form (developed for participants 8 to 14 years old) and a proxy completed paediatric form (developed for participants <15 years old));
- FOP assistive devices assessment.

### 9.2.7.3 Follow-up Visits/End of Study Visit for Exposed Participants

The participants will attend a clinic or telephone/video visit and assessments will be performed according to routine clinical care. For the FOPal registry study, the following variables will be captured from medical records as available:

- Physical examination;
- Growth status assessment for growing children (bone age, knee height and epiphyseal status, assessment as per local label);
- Tanner staging for growing children;
- Linear height and weight;
- Vital signs (respiratory rate, blood pressure and heart rate);
- Pregnancy test (as per local label, pregnancy tests should be performed monthly while treatment with palovarotene is ongoing and one month after treatment is stopped) and change in fertility status;
- Concomitant medications;
- Concomitant surgery and non-drug therapies;
- Marketed palovarotene dose for chronic and flare-up treatment;
- Spirometry and DLCO test;
- CAJIS for FOP;
- Number of flare-ups since Last Visit;
- Movement mobility changes;
- Spinal health assessment using radiological imaging (e.g. CT, X-ray, scintigraphy, etc);
- AEs, SAEs, Special Situations, and AESIs;
- FOP-PFO:
- PROMIS Global Health Scale;
- FOP assistive devices assessment.

**PAGE 49 OF 287** 

#### 9.2.7.4 Follow-up Visits/End of Study Visit for Unexposed Participants

The participants will attend a clinic or telephone/video visit and assessments will be performed according to routine clinical care. For the FOPal registry study, the following variables will be captured from medical records as available:

- Physical examination;
- Growth status assessment for growing children (bone age, knee height and epiphyseal status, assessment as per local label);
- Tanner staging for growing children;
- Linear height and weight;
- Vital signs (respiratory rate, blood pressure and heart rate);
- Concomitant medications;
- Concomitant surgery and non-drug therapies;
- Spirometry and DLCO test;
- CAJIS for FOP;
- Number of flare-ups since Last Visit;
- Movement mobility changes;
- Medical events of special interest;
- FOP-PFQ;
- PROMIS Global Health Scale;
- FOP assistive devices assessment.

# 9.2.8 Registry Study Discontinuation/Withdrawal

The participant can withdraw (or be withdrawn if the subject is a child upon legal representative's decision) from the FOPal registry study at any time. The date and primary reason for withdrawal should be recorded in the eCRF as well as whether the participant stopped or not palovarotene for exposed participants.

Should the participant withdraw from the study, no further data will be collected, nevertheless, data collected up to the time of the withdrawal will be kept for analysis, safety and integrity of study results.

The participant will be withdrawn from the FOPal registry study if:

- The participant enrols in any interventional clinical trial for FOP, or,
- For exposed participants: the participant is no longer receiving palovarotene (except if palovarotene is discontinued due to a safety concern or pregnancy, in such cases the participant will be monitored for safety, see Section 11.4 for follow-up of AEs and Section 11.1.3.1 for follow-up of pregnancies).
- For unexposed participants: the participant becomes pregnant or starts a treatment for FOP other than palovarotene. In case the participant starts palovarotene, they should have the option to remain in the registry. Previously unexposed participants starting palovarotene and remaining in the registry will follow the exposed naïve participants schedule (Table 2) from the first marketed palovarotene intake.

Investigators, participants or/and parents may decide to stop the participation in the FOPal registry study at any time without consequences on the normal participant clinical care.

PAGE 50 OF 287

# 9.2.9 Treatment Discontinuation (Palovarotene)

Palovarotene treatment may be discontinued in the event of any AEs (see Section 11.1.1 for definition), SAEs (see Section 11.1.2 for definition), Special Situations (see Section 11.1.3 for definition), or AESIs (see Section 11.1.4 for definition) deemed by the investigator to warrant treatment discontinuation. In the event of pregnancy, palovarotene treatment must be discontinued (see Section 11.1.3.1).

Discontinuation of treatment due to AEs should be distinguished from discontinuation/withdrawal from the registry study due to participant/parent decision or end of follow-up.

If AEs or their sequelae (any AE, based on the investigator's opinion, not only those assessed as related) persist after the date of palovarotene discontinuation, the investigator must ensure that the participant receives appropriate medical follow-up and this should be properly documented in the participant's medical records.

All participants discontinuing palovarotene treatment will be followed up to 30 days after last palovarotene intake (unless consent is withdrawn).

## 9.2.10 Early Registry Study Termination

The sponsor can decide at any time to discontinue the FOPal registry study for any reason. Investigators will be informed of the decision. Ethics committees and Competent Authorities (CAs) will also be informed if required by local regulations.

## 9.3 Endpoints and Variables

## 9.3.1 Endpoints

# 9.3.1.1 Primary Endpoints

- Incidence and description of all TEAEs, whether or not they are considered as related to palovarotene;
- Incidence and description of all serious TEAEs, whether or not they are considered as related to palovarotene;
- Incidence and description of all nonserious TEAEs whether or not they are considered as related to palovarotene;
- Incidence and description of all serious and nonserious treatment-related TEAEs.

# 9.3.1.2 Secondary Endpoints

For participants with FOP exposed and unexposed to palovarotene:

- Raw values and change from Baseline in CAJIS total score at each Follow-up Visit;
- Raw values and shift from Baseline in use of assistive devices and adaptations for daily living at each Follow-up Visit;
- Raw values and change from Baseline in % of worst score for total score, upper extremities subscore and mobility subscore using age-appropriate forms of the FOP-PFQ at each Follow-up Visit;
- Raw values and change from Baseline in observed and % predicted FVC at each Follow-up Visit;
- Raw values and change from Baseline in observed and % predicted FEV1 at each Follow-up Visit;
- Raw values and change from Baseline in absolute and % predicted FEV1/FVC ratio at each Follow-up Visit;

PAGE 51 OF 287

- Raw values and change from Baseline in observed and % predicted DLCO at each Follow-up Visit;
- Raw values and change from Baseline in physical and mental function (mean global physical and mental health score converted into T-scores) for participants ≥15 years old and overall QoL (mean total score converted into T-scores) for participants <15 years old using age-appropriate forms of PROMIS Global Health Scale at each Follow-up Visit;
- Annualised frequency of flare-ups, categorised by overall occurrence;
- Number of locations impacted by movement mobility change per participant annually and change from Baseline;
- Any movement mobility change (better movement/the same movement/slightly worse movement/moderately worse movement/severely worse movement) by body location and annually;
- Evolution of locations impacted by movement mobility change (how many times a location is impacted) per body location, annually and change from baseline;
- Movement mobility outcomes (change in extra bone growth and change in movement), causes, associated symptoms if preceded by a flare-up event by body location;
- Frequency, severity, outcome and descriptive characteristics of any fractures, overall and at each Follow-up Visit, categorised by location;
- Annualised frequency and descriptive characteristics of bone fractures, categorised by overall occurrence and location;
- Incidence of pregnancy.

For participants with FOP exposed to palovarotene who become pregnant while enrolled in FOPal:

- Pregnancy characteristics and outcomes;
- Pregnancy-related AEs through the first year postpartum;
- Birth and developmental outcomes through the infant(s)' first year of life.

For growing children with FOP exposed and unexposed to palovarotene:

- Raw values and change from Baseline in linear height and knee height velocity at each Follow-up Visit until skeletal maturity or final adult height is reached;
- Baseline linear height z-scores and change from Baseline at each Follow-up Visit until skeletal maturity or final adult height is reached;
- Mean difference between chronological age and bone age at each Follow-up Visit;
- Frequency, severity and descriptive details of PPC overall and at each Follow-up Visit.

For participants with FOP exposed to palovarotene:

- Mean dose/year for chronic treatment;
- Mean dose/cycle for flare-up treatment.

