**PAGE 39 OF 287** 

 Table 2
 Schedule of Assessments: Exposed Naïve Participants

Assessment/Procedure	Baseline Visit	Follow-Up Visits (as per routine clinical practice[a])/ End of Study Visit
Clinic visit or telephone/video contact visit	X	X
Informed consent [b]	X	
Inclusion/exclusion criteria	X	
Baseline demographics	X	
Physical examination [c,d]	X	X
Medical or surgical history	X	
FOP history	X	
Growth status assessment (bone age, knee height and epiphyseal status) [d,e]	X	X
Tanner staging [d,e]	X	X
Linear height [f] and weight [d]	X	X
Vital signs [d,g]	X	X
Pregnancy testing [h]	X	X
Prior /concomitant medications [i]	X	X
Concomitant surgery and non-drug therapies	X	X
Prior use of palovarotene (investigational product)	X	
Palovarotene dose for chronic and flare-up treatment [j]	X	X
Spirometry and DLCO test [d,k]	X	X
CAJIS [d]	X	X
Movement mobility history (including flare-ups [1])	X	
Movement mobility changes (including flare-ups)	X	X
Spinal health assessment [m]	X	X
AEs, SAEs, Special Situations, and AESIs [n]	X	X
Participant Questionnaires:		
FOP-PFQ assessment [o]	X	X
PROMIS Global Health Scale [o]	X	X
FOP assistive devices assessment [o]	X	X

AE=Adverse Event; AESI=Adverse Event of Special Interest; CAJIS=Cumulative Analogue Joint Involvement Scale; CT= Computed Tomography; DLCO=Diffusion Capacity of the Lung for Carbon Monoxide; FEV1=Forced Expiratory Volume in one second; FOP=Fibrodysplasia Ossificans Progressiva; FOP-PFQ=FOP-Physical Function Questionnaire; FVC=Forced Vital Capacity; HEENT= head, eyes, ears, nose and throat; PI=Prescribing Information; PROMIS=Patient-Reported Outcomes Measurement Information System; SAE=Serious Adverse Event; SS=Special Situation.

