**PAGE 40 OF 287** 

- a Follow-up Visits are recommended every 6 months, or as per local label.
- b If participant <18 years (or the legal age of consent in the jurisdiction in which the study is taking place), assent and parent or legally authorised representative consent will also be required.
- c This includes a general assessment, dermatologic, lymph nodes, HEENT, chest, cardiac, abdomen, limb/extremities, musculoskeletal, neurologic and other.
- d Not expected in the context of a telephone/video visit.
- e Collected for growing children. Assessment as per local label.
- f Linear height within 6 to 12 months prior to and at the Baseline Visit.
- g Vital signs to be collected are respiratory rate, blood pressure and heart rate.
- h Participants will be assessed for child-bearing status and pregnancy prevention measures. As per local label, pregnancy testing is carried out with a confirmation of absence of pregnancy monthly if the participant receives palovarotene and one month after stopping. These conditions also concern participants who are not currently sexually active unless the prescriber considers that there are compelling reasons to indicate that there is no risk of pregnancy.
- i This includes a period of two months prior to the signed informed consent date.
- i Not applicable for pregnant participants.
- k Spirometry obtains the lung function parameters of observed and % predicted FVC and FEV1 and the absolute and % predicted FEV1/FVC ratio. The DLCO test obtains observed and % predicted DLCO which provides information on the efficiency of gas transfer from alveolar air into the bloodstream.
- 1 This includes number of flare-ups over the past 12 months before the signed informed consent date.
- m Spinal health assessment to be performed using radiological imaging (e.g. CT, X-ray, scintigraphy, etc).
- n AE, SAE, Special Situation and AESI collection begins once the informed consent has been signed.
- o Paper-based patient-reported questionnaires.

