**PAGE 44 OF 287** 

- \* Retrospective period starts 12 months preceding the signed informed consent but only from the time the child has reached the age of 8 years for girls and 10 years for boys.
- a Follow-up Visits are recommended every 6 months.
- b If participant <18 years (or the legal age of consent in the jurisdiction in which the study is taking place), assent and parent or legally authorised representative consent will also be required.
- c This includes a general assessment, dermatologic, lymph nodes, HEENT, chest, cardiac, abdomen, limb/extremities, musculoskeletal, neurologic and other.
- d Not expected in the context of a telephone/video visit.
- e Collected for growing children.
- f Vital signs to be collected are respiratory rate, blood pressure and heart rate.
- g Spirometry obtains the lung function parameters of observed and % predicted FVC and FEV1 and the absolute and % predicted FEV1/FVC ratio. The DLCO test obtains observed and % predicted DLCO which provides information on the efficiency of gas transfer from alveolar air into the bloodstream.
- h Paper-based patient-reported questionnaires.
- i Closest available value to 12 months preceding signed informed consent.
- j Previously unexposed participants starting palovarotene and remaining in FOPal should follow the exposed naïve participants schedule from the first marketed palovarotene intake (See Table 2 and Section 9.2.8).

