#### **Growth Status**

Height, bone age, skeletal maturity and epiphyseal status will be analysed for growing children (paediatric).

Linear height velocity, linear height z-scores, knee height velocity, and chronological age will be derived for growing children. Annualised height velocity will be derived once two consecutive measurements are spaced by a minimum of 6 months and a maximum of 12 months.

Actual values and changes from the Baseline Visit in linear height and knee height velocity and the difference between chronological age and bone age will be presented at each visit. Linear height z-scores and change from Baseline until final adult height (defined clinically as last height velocity <1cm/year or radiologically as closed epiphysis of hand-wrist or knee) is achieved will be presented at each visit. The frequency, severity and descriptive details of PPC in growing children will also be presented overall.

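### For children enrolled directly as exposed naïve, change from Baseline in knee height velocity has no starting value, because the protocol requests an earlier measurement for linear height only

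*Protocol*

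**What the plan says.** Protocol section 9.3.1.2 sets the endpoint for growing children in both cohorts: "Raw values and change from Baseline in linear height and knee height velocity at each Follow-up Visit until skeletal maturity" or final adult height. Section 9.7.3.4 (Growth Status) repeats it as the planned analysis at each visit, without a condition: "Actual values and changes from the Baseline Visit in linear height and knee height velocity". The same section gives the only derivation rule: "Annualised height velocity will be derived once two consecutive measurements are spaced by a minimum of 6 months and a maximum of 12 months".

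The measurements requested differ by group.

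- **Exposed naïve (Table 2).** There is no retrospective column. Knee height belongs to the growth status row, marked at the Baseline Visit and at follow-up. Note f adds an earlier value for one variable: "Linear height within 6 to 12 months prior to and at the Baseline Visit". Section 9.2.7.1 says the same: "linear height within 6 to 12 months prior to the Baseline Visit will also be collected". Section 9.3.2.4 also limits the earlier value to linear height, and the Growth Status text in 9.3.2.7 gives no knee height before Baseline for naïve children.
- **Exposed non-naïve (Table 3).** Note p limits retrospective growth status to the first marketed intake. Note f again requests an earlier value, before first intake, for linear height only.
- **Unexposed (Table 4).** The whole growth status row, knee height included, is requested retrospectively under note i: "Closest available value to 12 months preceding signed informed consent".

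**The concern.** A change from Baseline in a velocity needs a velocity at Baseline, and that needs two measurements, one of them taken earlier. The protocol provides for this with linear height but does not carry it over to knee height, although the endpoint treats the two alike.

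Knee height velocity is one of the growth measures for a drug with a known growth-plate signal: section 7.3.1 reports premature physeal closure in 13 of 39 participants (33%) aged from 8/10 to under 14 years. Children who enter before their first dose are the ones in whom growth before and after the start of treatment could be contrasted. For them this part of the endpoint has no planned starting value. A statistical analysis plan cannot repair that, because it cannot derive a value that the case report form never requested.

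**Working it through.** The protocol gives no figure to reproduce on this point. The check counts the measurements each schedule yields and applies the protocol's own rule.

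**Rule.** With heights K1 and K2 (any length unit) at months t1 and t2:

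- velocity = 12 × (K2 − K1) / (t2 − t1) per year, allowed only if 6 ≤ t2 − t1 ≤ 12;
- change from Baseline at a visit = velocity at that visit − velocity at the Baseline Visit (month 0).

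The second line needs a measurement between month −12 and month −6 as well as one at month 0.

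**Measurements available by the Baseline Visit, as scheduled**

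| Group and variable | Measurements requested | Count | Baseline velocities |
|---|---|---|---|
| Exposed naïve, linear height | between months −12 and −6; month 0 | 2 | 1 |
| Exposed naïve, knee height | month 0 | 1 | 0 |
| Exposed non-naïve, knee height | first marketed intake; month 0 | 2 | at most 1, on treatment |
| Unexposed, knee height | about month −12 if available; month 0 | up to 2 | up to 1, without treatment |

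**Exposed naïve.** With visits at the recommended 6-month spacing, knee heights fall at months 0, 6 and 12. The first velocity covers months 0 to 6 and the second months 6 to 12. Both are usable as raw values. Neither is a Baseline velocity, so the subtraction cannot be made at any visit. Because palovarotene has been prescribed before enrolment (section 9.2.1.1), the first interval is essentially on treatment.

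**Exposed non-naïve.** The two measurements give a Baseline velocity only if first intake and the Baseline Visit are 6 to 12 months apart. For example, a 20-month gap fails the rule and a 9-month gap meets it. Where a velocity exists it lies wholly on treatment. No pre-treatment knee height velocity can be formed, because nothing before first intake is requested. The protocol does not give the expected gap, so the share of non-naïve children with a Baseline velocity is unknown.

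**Unexposed.** Values at months −12 and 0 give a velocity. It is possible rather than assured, for three reasons: the value is whatever lies closest to 12 months back and may fall outside the 6 to 12 month window; the retrospective period is cut off below age 8 (girls) or 10 (boys); and the retrospective knee height appears in Table 4 but not in the lists of sections 9.2.7.2 and 9.3.2.7.

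**Number of children.** Half of 67 is 33.5. That counts all paediatric exposed participants. Knee height is collected only in those with unfused growth plates, and the naïve/non-naïve split is not stated. The affected number is therefore some unknown part of about 33.

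**After the fix.** One knee height between months −12 and −6 gives a naïve child 2 measurements and 1 Baseline velocity. Change from Baseline then exists from the first follow-up visit at least 6 months later.

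**The case against.** The strongest reply is that little depends on this. In the exposed/unexposed comparison (section 9.7.3.4) the growth measures are linear height velocity and height z-scores, with knee height optional according to what data exist. Linear height has its earlier value. Premature physeal closure, epiphyseal status and bone age are recorded directly and do not depend on knee height velocity. Analyses are descriptive, only routine-care data are captured, and the limitations section accepts that some data will be missing. All of this stands, and it keeps the point minor. It does not remove it: the availability condition applies to the comparison only, whereas the endpoint in 9.3.1.2 and its analysis carry none. The value is also not merely likely to be missing. It is not requested, even where a site holds it.

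Three stronger readings are tempting, and the documents do not support them.

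- *No child on the naïve schedule can have a Baseline knee height velocity.* Unexposed participants who start palovarotene move to that schedule (Table 4 note j, section 9.2.8) and may already have registry knee heights, so a pre-treatment velocity can exist for them. The gap concerns children enrolled directly as exposed naïve.
- *The endpoint is underivable for non-naïve children.* It is defined against the Baseline Visit, which is on treatment for them in every change-from-Baseline endpoint. A Baseline velocity can exist; what is lacking is a pre-treatment one.
- *The plan will use the first on-treatment velocity as Baseline.* The protocol nowhere says so.

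**Conclusion.** The point holds in a limited form. For growing children enrolled directly as exposed naïve, the schedule yields one knee height and no knee height velocity by Baseline, so the stated change from Baseline has no starting value. Raw velocities after Baseline remain derivable. A treatment-free Baseline velocity is possible mainly in the unexposed cohort, without being assured there.

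A reader might infer that about 33 children are affected, or that the unexposed cohort reliably has the missing value. The first figure is only an upper limit, and the second depends on what older records contain.

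The conclusion assumes that the 6 to 12 month rule in section 9.7.3.4 applies to knee height as it does to linear height. No other rule is given. Severity is minor: a secondary, descriptive endpoint is incomplete in one group, while linear height velocity, premature physeal closure and bone age are unaffected.

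**What to change.** Extend note f of Tables 2 and 3, and the matching text in sections 9.2.7.1, 9.3.2.4 and 9.3.2.7, to knee height. Record any routine knee height taken 6 to 12 months before the Baseline Visit (naïve) or before first marketed intake (non-naïve), if available. Where none exists, report raw knee height velocity only, and do not treat an on-treatment velocity as a pre-treatment Baseline.

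The cost is one retrospective case report form field, filled from existing records with no new test, and one sentence on its use in the analysis. Some children will have no earlier value, and the yield cannot be predicted from the protocol. Enrolment may run up to 10 years from the first participant's first visit, so the earlier the change is made, the more children it covers.
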